#### 8.6.7 REPORTING EVENTS TO PARTICIPANTS

Participants who experience adverse events will be followed until resolution, and will be referred for consultation as needed.

---

### 8.7 UNANTICIPATED PROBLEMS

---

#### 8.7.1 DEFINITION OF UNANTICIPATED PROBLEMS (UP)

The Office for Human Research Protections (OHRP) considers unanticipated problems involving risks to participants or others to include, in general, any incident, experience, or outcome that meets **all** of the following criteria:

- Unexpected in terms of nature, severity, or frequency given (a) the research procedures that are described in the protocol-related documents, such as the Institutional Review Board (IRB)-approved research protocol and informed consent document; and (b) the characteristics of the participant population being studied;
- Related or possibly related to participation in the research (“possibly related” means there is a reasonable possibility that the incident, experience, or outcome may have been caused by the procedures involved in the research); and
- Suggests that the research places participants or others at a greater risk of harm (including physical, psychological, economic, or social harm) than was previously known or recognized.

---

### 8.7.2 UNANTICIPATED PROBLEM REPORTING

The investigator will report unanticipated problems (UPs) to the Institutional Review Board (IRB). The UP report will include the following information:

- Protocol identifying information: protocol title and number, PI’s name, and the IRB project number;
- A detailed description of the event, incident, experience, or outcome;
- An explanation of the basis for determining that the event, incident, experience, or outcome represents an UP;
- A description of any changes to the protocol or other corrective actions that have been taken or are proposed in response to the UP.

To satisfy the requirement for prompt reporting, UPs will be reported using the following timeline:

- UPs that are serious adverse events (SAEs) will be reported to the IRB and to the study sponsor within 72 hours of the investigator becoming aware of the event.
- Any other UP will be reported to the IRB and to the study sponsor within 7 days the investigator becoming aware of the problem.
- All UPs should be reported to appropriate institutional officials (as required by an institution’s written reporting procedures), the supporting agency head (or designee), and the Office for Human Research Protections (OHRP) within of the IRB’s receipt of the report of the problem from the investigator.

---

### 8.7.3 REPORTING UNANTICIPATED PROBLEMS TO PARTICIPANTS

Participants who experience adverse events related to unanticipated problems will be followed until resolution, and will be referred for consultation as needed.

## 9 STATISTICAL CONSIDERATIONS

### 9.1 STATISTICAL ENDPOINTS

#### Primary Endpoint: Safety

- Determination of safety

#### Secondary Endpoints: Blood and CSF biomarkers of drug pharmacodynamic effect

- Day 7 serum EET/DHET ratio
- Day 7 CSF EET/DHET ratio
- Day 7 CSF inflammatory cytokines
- Day 7 serum endothelial injury biomarkers
- Day 7 serum EPOME/DPOME ratio
- Day 10 serum EET/DHET ratio
- Day 10 CSF EET/DHET ratio
- Day 10 CSF inflammatory cytokines
- Day 10 serum endothelial injury biomarkers
- Day 10 serum EPOME/DPOME ratio

#### Tertiary Endpoints: Clinical endpoints

- Incidence of neurologic changes attributable to DCI
- Incidence of angiographic vasospasm
- Incidence of new stroke at hospital discharge
- Hospital length of stay
- Hospital discharge Modified Rankin Scale score
- Hospital discharge disposition
- 90-day follow-up Modified Rankin Scale score
- 90-day follow-up Glasgow Outcome Scale Extended score

## 9.2 SAMPLE SIZE DETERMINATION

The total sample size was selected *a priori* based on the need to evaluate and describe the safety profile of the study drug in this patient population.

## 9.3 POPULATIONS FOR ANALYSES

Any patient who receives a single dose of study drug will be included in safety analyses as part of the safety population. Only patients who complete 10 days of study drug administration will be included in the secondary analyses as part of the per-protocol population.

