**Justification:** EETs are degraded to inactive byproducts DHETs by the enzyme sEH. sEH activity has previously been measured after exposure to the study drug, and found to reach steady state level of >95% drug inhibition at 7 days. Prior evaluations of drug efficacy have used indirect means to measure drug effectiveness in inhibiting exogenous EETs degradation. We will directly measure *in vivo* EETs levels after drug administration to determine the degree by which sEH inhibition results in measurable increases in systemic EETs. Endogenous EETs have a very short half-life and require rapid sample processing and meticulous storage conditions.

We have chosen to measure the EET/DHET ratio due to the normal fluctuations of EETs levels in the post-bleed period after SAH. The drug will be deemed effective if we measure higher EET/DHET ratio in the treatment group compared to placebo, i.e. higher EETs suggests decreased metabolism by sEH. It is possible that serum EET/DHET ratio will not be measurably increased. EETs have a very short serum half-life (minutes), and the most plausible site of action is at the neurovascular unit.

To more precisely estimate sEH enzyme activity in plasma, we will also measure the metabolism of more stable lipid substrates of sEH: EPOME, and the metabolic byproduct DPOME. Serum EPOME and DPOME levels have previously been used to measure the hydrolase activity of sEH.[13]

We will also determine whether there are CNS effects of the drug, either via direct measurement of increased EET/DHET ratio in the CSF, or via downstream effects on the inflammatory profile in the CSF and on the markers of endothelial dysfunction. This is particularly important because in healthy subjects and animals, the drug does not cross the blood brain barrier. It is possible that EETs have a localized action on the endothelium and vascular smooth muscle, without crossing the blood brain barrier. sEH inhibition may exert anti-inflammatory and vasodilatory effects at this site without changing measurable CSF EETs levels. If this is the case, we expect to detect differences in CSF inflammatory markers.

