### 7 STUDY INTERVENTION DISCONTINUATION AND PARTICIPANT DISCONTINUATION/WITHDRAWAL

#### 7.1 DISCONTINUATION OF STUDY INTERVENTION

Discontinuation from drug or placebo administration does not mean discontinuation from the study, and remaining study procedures should be completed as indicated by the study protocol. All patients are expected to complete the treatment course unless they experience an SAE that is thought to be related to the study drug, die, are discharged early, or withdraw early from the study.

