## 8.5 PHARMACODYNAMIC EFFECT ASSESSMENTS

### 8.5.1 SAMPLE COLLECTION

Blood samples will be collected from study participants after randomization but prior to administration of the first dose of study drug or placebo, and again on study day 7 and study day 10. For patients with an external ventricular drain (EVD), cerebrospinal fluid (CSF) will be collected at each timepoint as well.

10 mL of blood and 5 mL of CSF will be collected at each time point. If the indwelling external ventricular drain is removed prior to study day 10, CSF samples will be collected on the day of planned removal. In the event of inability to collect CSF due to obstructed catheter, or low intracranial CSF volume, one additional attempt will be allowed within a period of 24 hours.

Blood samples will be collected by the bedside nurse and processed for storage by study personnel. CSF samples will be collected by physician medical staff, from external ventricular drainage access, and then processed for storage by study personnel.

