#### 9.4.4 ANALYSIS OF THE SECONDARY AND TERTIARY ENDPOINTS

Secondary endpoints will be compared between the study drug and placebo groups using the per-protocol population. Serum and CSF EET/DHET ratios and biomarkers will be presented as

the mean and standard deviation, and differences evaluated with two sample Student's t-test with a two-sided type 1 error rate of 0.05%.

Tertiary endpoints will be compared descriptively between the groups based on the mean, median, standard deviation and range.

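### The five Day 7 pharmacodynamic endpoints are limited to 10-day completers, so a valid on-treatment Day 7 sample is dropped if dosing stops on Days 8-10

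*Combined protocol and SAP*

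**What the plan says.** Section 9.3 sets the population: "Only patients who complete 10 days of study drug administration will be included in the secondary analyses as part of the per-protocol population". Section 9.4.4 applies it without exception: "Secondary endpoints will be compared between the study drug and placebo groups using the per-protocol population".

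Section 9.1 lists five Day 7 secondary endpoints, beginning with "Day 7 serum EET/DHET ratio". The others are the CSF EET/DHET ratio, CSF cytokines, serum endothelial injury markers and the serum EPOME/DPOME ratio. Each is repeated at Day 10. None has its own population rule.

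Section 3 says that enzyme activity under the drug was "found to reach steady state level of >95% drug inhibition at 7 days".

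Section 7.1 keeps patients who stop dosing in the study: "Discontinuation from drug or placebo administration does not mean discontinuation from the study, and remaining study procedures should be completed as indicated". Besides a drug-related SAE, it expects the course to be cut short only when patients "die, are discharged early, or withdraw early from the study".

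Section 8.5.1 limits CSF to patients with a drain: "For patients with an external ventricular drain (EVD), cerebrospinal fluid (CSF) will be collected at each timepoint as well".

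Section 9.4.1 says in general terms that the analysis will be presented for everyone who received at least one dose. This does not match the specific rule in 9.3 and 9.4.4.

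**The concern.** A Day 7 sample cannot be altered by what happens on Days 8-10. The plan nevertheless makes its use depend on those days. The usual reason for a per-protocol set is to avoid dilution by patients who were not on drug. That reason does not apply to someone dosed up to the Day 7 draw.

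Two things are at stake. First, usable on-treatment data are discarded in a trial of up to 30 patients. Second, the reasons for late stopping (drug-related SAE, death, early discharge, withdrawal) may relate to severity or to treatment. If late stopping differs between arms in rate or cause, the Day 7 contrast is biased by selection after the measurement.

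These endpoints matter beyond description: section 3 says the drug will be judged effective on the EET/DHET comparison. The concern is confined to Day 7. An on-treatment set at Day 10 is not disputed.

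**Working it through.** **1. Reading the rule.** Samples are taken at baseline, Day 7 and Day 10 (8.5.1). A patient dosed on Days 1-7, sampled on Day 7 and stopped on Day 8 has not completed 10 days. That patient is outside the per-protocol population (9.3) and so outside all five Day 7 comparisons (9.4.4). Sections 9.4.1 and 9.4.2 report exclusions and missing-data patterns but do not restore the sample.

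**2. No figure to reproduce.** Section 9.2 bases the sample size on describing safety and gives no power, effect size or dropout rate.

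**3. Inputs.**
- From the documents: up to 30 patients, equally randomised (4.1), so 15 per arm nominally.
- Assumed: non-completion q = 10%, 20% or 30%; share f = 30-50% of non-completers stopping after Day 7; effect d = 1.06 SD (80% power at 15 per arm); two-sided 5%. Section 9.4.4 prints 0.05%, which is taken here as 5%.

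**4. Patients affected** = 30 × q × f. At q = 20%: 30 × 0.20 × 0.30 = 1.8, up to 30 × 0.20 × 0.50 = 3.0.

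**5. Power.** Completers per arm: 15(1 − q). Day 7 on-treatment set: 15(1 − q) + 15qf. Two-sample t-test with 2n − 2 degrees of freedom and noncentrality d√(n/2):

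| q | Affected of 30 | n per arm: completers / Day 7 set | Power: completers / Day 7 set |
|---|---|---|---|
| 10% | 0.9-1.5 | 13.5 / 13.95-14.25 | 75% / 77-78% |
| 20% | 1.8-3.0 | 12 / 12.9-13.5 | 70% / 73-75% |
| 30% | 2.7-4.5 | 10.5 / 11.85-12.75 | 64% / 69-73% |

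Variations at q = 20%:
- d = 0.8: 47% against 50-52%.
- d = 1.3: 86% against 89-90%.
- 12:18 split: 68% against 72-74%. Unrestricted randomisation (6.3) gives a split at least this uneven among 30 with probability 0.36.
- Alpha read literally as 0.0005: 11% against 13-15%.

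**6. Precision.** The 95% half-width in SD units is t(0.975, 2n − 2) × √(2/n). At n = 12: 2.074 × 0.408 = 0.85. At n = 12.9-13.5: 0.81-0.79.

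**7. CSF,** assuming 50-80% of patients have a drain, q = 20%:
- 50% (n = 6 against 6.45-6.75): power 38% against 41-43%; half-width 1.29 against 1.23-1.19 SD.
- 80% (n = 9.6 against 10.32-10.8): power 59% against 63-65%; half-width 0.96 against 0.92-0.90 SD.

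**8. Bias.** Simulation with no true effect, 4 million patients per arm, stopping logistic in severity (slope 1), and marker-severity correlation 0.3 or 0.7. Earlier stopping is 10% in both arms:

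| Late stopping by arm | Completer bias, SD (corr. 0.3 / 0.7) |
|---|---|
| 10% v 10% | about 0 |
| 10% v 5% | 0.013 / 0.032 |
| 15% v 5% | 0.025 / 0.061 |
| 20% v 5% | 0.037 / 0.090 |

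The Day 7 set shows at most 0.002 SD throughout. The standard error at n = 12 is √(2/12) = 0.41 SD. If total non-completion differs (30% v 15% up to 40% v 10%), completer bias is 0.04-0.17 SD. The Day 7 set then removes 0.02-0.11 SD and leaves 0.01-0.09 SD.

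**The case against.** The textual point is not in dispute. The case against it is about consequence.

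- **Every magnitude is assumed, and the gain is 3-5 power points in the central case,** on secondary endpoints of a phase 1b trial not sized for them. This stands. If nobody stops on Days 8-10, the gain is zero.
- **The larger bias cases exceed the assumed 30-50% late share.** This also stands. With 10% early stopping, 15% and 20% late stopping make late stoppers 15/25 = 60% and 20/30 = 67% of that arm's non-completers. Only the 10% v 5% case fits, giving 0.01-0.03 SD. The others are stress cases.
- **The Day 7 set looks unbiased because earlier stopping was set equal.** Correct. That set still conditions on dosing after randomisation, so it removes the part due to Days 8-10 and no more.
- **CSF is hit no harder than blood.** In power points this is true. In precision it is not: the half-width falls by 0.06-0.09 SD (50% with a drain) or 0.04-0.06 SD (80%), against 0.03-0.05 SD for blood.
- **Section 9.4.1 already covers all dosed patients.** It leaves room for such a presentation, but it is general, while 9.3 and 9.4.4 are specific and exclusive. Two rules that disagree leave the analyst a choice.
- **Completing 10 days is undefined for missed or late doses,** which 6.1.2 allows to be given late. This stands, and a Day 7 set inherits it unless the wording deals with it.

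**Conclusion.** The concern holds. As written, the plan discards valid on-treatment Day 7 samples because of later events, and no other section restores them. The correction should be made, but the expected effect is modest. Under the central assumptions about 2-3 of 30 patients are affected, power rises from 70% to 73-75%, and the half-width falls from 0.85 to 0.79-0.81 SD. Bias is small against the standard error: 0.01-0.03 SD within the assumed late-stopping share, up to 0.09 SD beyond it, and about zero if late stopping is alike in both arms. Because the completion rate, stopping times, drain rate and effect size are all assumed, the case rests mainly on the logic of the rule.

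**What to change.** In 9.3 and 9.4.4, define the on-treatment set by time point:

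- **Day 7:** all randomised patients whose study drug was not stopped before the Day 7 sample and who have that sample, by assigned arm. State how missed or late doses count for membership.
- **Day 10:** the 10-day-completer set may stay.
- **Supportive, both time points:** all randomised patients with at least one dose and a sample at that time point, by assigned arm.

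Align the general statement in 9.4.1. Section 8.5.1 says "If the indwelling external ventricular drain is removed prior to study day 10, CSF samples will be collected on the day of planned removal"; state which time point such a sample counts for. Report the number sampled per arm at each time point, separately for blood and CSF.

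**Cost.** Wording only: no added patients, visits or assays. The main Day 7 set adds no dilution, since everyone in it was on drug when sampled. The supportive set does dilute. If stoppers lose the whole effect, at 20% non-completion its Day 7 power is 67-71% with all earlier stoppers sampled and 70-73% with half sampled, against 70% for completers. At 30% non-completion with all sampled it is 60-66% against 64%. At Day 10, with 20% non-completion, it is 65-67% if 0.9-1.5 stoppers per arm are sampled and 61% if all are. Section 2.2 reports inhibition lasting up to 48 hours after repeat dosing, so full loss overstates the dilution for recent stoppers. The set should remain supportive. Patients without a sample stay missing.

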## 9.4 STATISTICAL ANALYSES

### 9.4.1 GENERAL APPROACH

The statistical analysis performed for this study will be presented for all patients who receive at least 1 dose of the study drug. There will be no *a priori* stopping rules, since the entire sample is required to evaluate safety. However, the study can be stopped at any time for reasons related to safety concerns. The statistical analyses will be performed using STATA® version 13 or later (STATA Corp, College Station TX).

The number of participants included in each analysis set will be summarized, along with the reason for any exclusions. Participants discontinuing from study treatment and/or withdrawing from study participation the primary reason for discontinuation will be summarized.

Descriptive summaries of demographic and baseline characteristics will be tabulated for all participants.

---

#### 9.4.2 MISSING VALUES

Study investigators will monitor the study to maximize completion of data collection and samples. Every effort will be made to retain subjects to follow up. Patterns of missing data will be evaluated for the presence of informative missingness or if missing data are missing completely at random or at random.

---

#### 9.4.3 ANALYSIS OF THE PRIMARY ENDPOINT

Safety will be assessed by clinical review of all relevant parameters including vital signs, laboratory values, adverse events, serious adverse events, disease related events, and mortality. Unless specified otherwise, the safety analyses will be conducted for the safety population.

Summary tables and listings will be provided for all reported adverse events, defined as adverse events that start on or after the first administration of study drug. The reported adverse event term will be assigned a standardized preferred term.

Adverse events will be summarized based on the number and percentage of patients experiencing the event. In the event a patient experiences repeat episodes of the same adverse event, then the event with the highest severity grade and strongest causal relationship to study treatment will be used for purposes of incidence tabulations. Tabular summaries will be provided for all adverse events, the relationship to study drug treatment the maximum severity grade, action taken, and whether the event qualified as SAE or not.

Daily safety laboratory test results will be summarized in a descriptive manner by calculating the mean, standard deviation, median, and range. Directional shifts (comparing baseline grade with worst post-baseline grade) will be analyzed using standard shift tables. The shift table will present directional shifts from baseline to above or below the laboratory standard normal range using the maximum increase and/or decrease observed throughout the course of treatment/observation.

Vital signs will be summarized in a descriptive manner by calculating the mean, standard deviation, median, and range in the same manner described for laboratory values.

All deaths will be reported in a patient listing, which will include the primary cause of death and the number of days between the date of the last dose of study drug and death.

---

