#### 8.6.4 TIME PERIOD AND FREQUENCY FOR EVENT ASSESSMENT AND FOLLOW-UP

The occurrence of an adverse event (AE) or serious adverse event (SAE) may come to the attention of study personnel during study visits and interviews of a study participant presenting for medical care, or upon review by a study monitor.

All AEs including local and systemic reactions not meeting the criteria for SAEs will be captured on the appropriate case report form (CRF). Information to be collected includes event description, time of onset, clinician’s assessment of severity, relationship to study drug (assessed only by those with the training and authority to make a diagnosis), and time of resolution/stabilization of the event. All AEs occurring while on study must be documented appropriately regardless of relationship. All AEs will be followed to adequate resolution.

Any medical condition that is present at the time that the participant is screened will be considered as baseline and not reported as an AE. However, if the study participant’s condition deteriorates at any time during the study, it will be recorded as an AE.

Changes in the severity of an AE will be documented to allow an assessment of the duration of the event at each level of severity to be performed. AEs characterized as intermittent require documentation of onset and duration of each episode.

Research staff will record all reportable events with start dates occurring any time after informed consent is obtained until 28 days post randomization or hospital discharge, whichever comes sooner. At each study visit, the investigator will inquire about the occurrence of AE/SAEs since the last visit. Events will be followed until resolution or stabilization.

---

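### The start-date rule in 9.4.3 leaves out of the AE tables a non-fatal event that begins between consent and first dose and then worsens on drug

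*Combined protocol and SAP*

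**What the plan says.** Section 9.4.3 sets the rule for the AE output: "Summary tables and listings will be provided for all reported adverse events", which it then narrows to those "defined as adverse events that start on or after the first administration of study drug". The start date is the only test. Nothing is said about an event that began earlier and got worse after dosing.

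Section 8.6.4 sets the rules for collection:

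- Staff record events with "start dates occurring any time after informed consent is obtained until 28 days post randomization or hospital discharge, whichever comes sooner", so events before the first dose are collected.
- "Information to be collected includes event description, time of onset", together with severity, relationship and resolution.
- "Changes in the severity of an AE will be documented to allow an assessment of the duration of the event" at each severity level. A worsening is thus a change within an existing AE.
- "Any medical condition that is present at the time that the participant is screened will be considered as baseline and not reported as an AE". But if the participant's "condition deteriorates at any time during the study, it will be recorded as an AE". The start date of that AE is not given.

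The first dose follows consent, randomization and baseline sampling (6.1.2) and is given immediately after randomization (8.3). Consent and enrollment must fall within 48 hours of admission to the unit (8.1).

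**The concern.** Safety is the primary endpoint, and patients are acutely ill when first dosed. Harm from a drug can show as aggravation of something that has already begun, as well as a new event. A rule that looks only at the start date does not see aggravation of an AE that began before dosing.

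Within 9.4.3, only the AE tables carry relatedness, maximum severity, action taken and SAE status. An event that is filtered out loses all four. The omission can only lower the counts. It applies to both arms.

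**Working it through.** The plan states no figure on this point, so there is none to reproduce. The main check is to apply the 8.6.4 and 9.4.3 rules to example records.

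| Record | Start date under 8.6.4 | In the 9.4.3 AE tables and listings? |
|---|---|---|
| A. Mild AE begins after consent and before first dose; becomes severe or serious on Day 3; not fatal | Before first dose, with a later severity change | No, unless the worsening is entered as a new AE |
| A, but fatal | As above | Not as an AE; the death is in the death listing |
| B. Condition present at screening; deteriorates on Day 4 | Not stated; most naturally Day 4 | Yes, if dated Day 4 |
| C. New event on Day 4 | Day 4 | Yes |

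**Record A.** The rule in 9.4.3 for repeat episodes, which keeps the highest severity, does not bring this record back. A worsening is not a repeat episode, and the record has already been filtered out.

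**Record B.** A condition present at screening is not an AE until it deteriorates. If the resulting AE took the original onset as its start, it would fall before consent and so outside the collection window, although 8.6.4 says it will be recorded. Dating it at the deterioration is therefore the coherent reading. Only the instruction is missing.

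**Size per omitted patient.** Inputs: up to 30 patients, equally randomized (4.1), so nominally 15 per arm. Because 6.3 specifies unrestricted fair-coin allocation, arms of 10 and 20 are shown as well; a split at least that uneven has a probability of about 10%. One affected patient per arm is an assumption. Intervals are exact (Clopper-Pearson): the lower limit is the 0.025 quantile of Beta(x, n−x+1), or 0 when x = 0, and the upper limit is the 0.975 quantile of Beta(x+1, n−x).

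| Arm size | Event counted | Event omitted | Drop |
|---|---|---|---|
| 10 | 1/10 = 10.0% (0.3–44.5%) | 0/10 = 0% (0–30.8%) | 10.0 points |
| 15 | 1/15 = 6.7% (0.2–31.9%) | 0/15 = 0% (0–21.8%) | 6.7 points |
| 20 | 1/20 = 5.0% (0.1–24.9%) | 0/20 = 0% (0–16.8%) | 5.0 points |

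The drop applies to a table row in which the patient has no other qualifying event. If one patient is lost from each of two arms of 15, both rates fall by 6.7 points and their difference is unchanged.

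**How often.** The documents give no rate. If a fraction q of patients has a type A event, the expected loss in an arm of 15 is 15q, and the chance of losing at least one is 1 − (1 − q)^15. Two assumed values:

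- q = 1%: 15 × 0.01 = 0.15 patients; 1 − 0.99^15 = 14%.
- q = 5%: 15 × 0.05 = 0.75 patients; 1 − 0.95^15 = 54%.

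The interval from consent to first dose contains only randomization and baseline sampling. The 48 hours in 8.1 run from admission and include time before consent. Even 5% has no support in the documents.

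**The case against.** The strongest reply is that little is lost. Several outputs in 9.4.3 ignore the AE start date: the listing of all deaths with cause, the laboratory shift tables from baseline to worst later value, and the vital-sign summaries. Section 9.4.3 also names disease-related events as a separate part of the safety review, and 8.4.2 logs them with their own onset times. The on-drug worsening is captured in the data, because severity changes are documented. Expedited SAE reporting (8.6.6) and ongoing monitoring (10.1.4) do not use the filter. The primary analysis is a clinical review with descriptive tables and no test. A dating instruction might also sit in the manual of procedures or the variable list, which are not part of the documents reviewed.

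Most of this stands, and it rules out two stronger readings that a reader might infer.

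- **That such an event disappears from every table and listing.** It does not: a fatal case is in the death listing, and a change in a daily laboratory value or a vital sign can show in those summaries.
- **That the rule heavily dilutes, or even erases, a true difference between the arms.** That would need worsening of conditions present at screening to be lost, and 8.6.4 makes those AEs in their own right. It would also need high rates of type A events, which a short window does not make plausible.

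What the reply does not remove is type A. The other outputs do not carry causality, maximum severity or SAE status. The deterioration sentence could be read as creating a new AE for type A as well. However, it follows a sentence about conditions present at screening, while the severity-change sentence points to a single record. Two programmers could build different AE tables from the same data.

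**Conclusion.** The point holds in a limited form and is minor. As written, 9.4.3 excludes from the AE and SAE summary tables and the AE listings a non-fatal AE that starts between consent and first dose and then increases in severity or becomes serious on drug, unless the worsening is entered as a new AE. For conditions present at screening, only the start date of the resulting AE is left unstated.

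Few events are expected. Each would lower the affected row by 6.7 percentage points in an arm of 15, or by 5 to 10 points in arms of 20 to 10. This rests on two assumptions: that a worsening stays within the original AE record, which is how 8.6.4 reads most directly, and that the patient has no other event in the same row. The number of affected patients cannot be derived from the documents.

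**What to change.** - **Section 9.4.3:** define the tabulated AEs as those that start, or that increase in severity or become serious, at or after the first dose. For a worsening, tabulate the severity, causality and seriousness that apply after dosing.
- **Section 8.6.4:** state that deterioration of a pre-dose condition or AE is entered with the date of deterioration as its start.
- **Listings:** show AEs that are wholly pre-dose separately.

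The cost is one sentence in 9.4.3 and one CRF completion instruction. Severity changes are already recorded. The date on which an event becomes serious is not among the items that 8.6.4 lists, so check that the CRF holds it. AE counts may rise slightly in both arms. Treatment, design and sample size are not affected.
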